Safety is an important first step and study outcome. In the published phase 2 and 3 studies of solriamfetol in patients with narcolepsy or obstructive sleep apnea (OSA), adverse events included headache (9-16%), nausea (12-14%), diarrhea (11%), decreased appetite (6-14%), anxiety (6-11%), chest discomfort (9%), insomnia (6%), muscle tightness (6%), nasopharyngitis (5-14%), and dry mouth (5-10%). Cancer patients and in particular brain tumor patients are at risk for some of these and other cognitive, seizure, or neurological toxicities that need to be explored at each of solriamfetol's three dose levels (75 mg, 150 mg, 300 mg) prior to proceeding to a primary efficacy endpoint. The current trial will establish this experience.

Prior studies of solriamfetol have shown early improvements in patient-reported sleep by ESS scores. In the current study we will also evaluate other associated symptoms of fatigue, neurocognition, mood, and quality of life. It is not clear that these associated symptoms will respond as quickly to drug therapy. In fact, according to our model of the sleep-fatigue-neurocognitive symptom cluster (Figure 1), we suspect that improvement in fatigue, neurocognition, mood and quality of life are downstream of the improvement in sleep and thus, in this study, endpoints will be assessed after prolonged stable drug therapy. This should not affect the ability to assess for improvements in sleep which have been reported as early as 1 week after solriamfetol treatment and remained stable over up to 12 weeks of continued treatment in the aforementioned studies.

2 Hypotheses

1. Primary Hypothesis

We hypothesize that the side effect profile of solriamfetol at doses of 75 mg daily, 150 mg daily, and 300 mg daily will be similar in patients with primary brain tumors to that reported in patients with narcolepsy and obstructive sleep apnea.

Serious adverse events in patients with primary brain tumors including significant confusion/ altered mental status, seizures, or other side effects will not be more common at the 300 mg daily dose compared to the 150 mg and 75 mg daily doses.

2. Secondary Hypotheses

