This is a single-arm, open label, two-part safety study of solriamfetol in patients with WHO grade 2-4 gliomas. Patients with stable disease by clinical examination and neuroimaging who have an ESS \geq 10 and meet all inclusion/exclusion criteria will be recruited and enrolled. First, all patients will receive solriamfetol at escalating doses. Second, all patients will complete a fixed dose drug continuation treatment at the patient-specific maximum tolerated dose.

The study will occur in 3 phases:

Open Label Safety Study of Solriamfetol to Promote Wakefulness and Improve Cognition and Quality of Life in
Patients with Primary Gliomas
Wake Forest Baptist Comprehensive Cancer Center
WFBCCC 98418

1. Pre-Treatment Baseline (~1 week)
2. Flexible Dose Titration (~3 weeks)
3. Fixed Dose Drug Continuation (~6 weeks)

Patients will initially complete a 1-week baseline actigraphy and sleep diary prior to treatment initiation to establish a baseline sleep pattern.

Solriamfetol will be dosed by flexible dose titration starting at 75 mg daily in all patients and escalating after 7 days (1 week) to 150 mg daily and then after 7 days to 300 mg daily for a total duration of 3 weeks (flexible dose titration period). Patients who experience a dose-limiting toxicity will be de-escalated to the last tolerated dose level and move to the fixed dose drug continuation phase. Prior studies incorporating this design have used a 3-day treatment prior to escalation.⁴⁹ For this study, 7 days has been selected to provide a sufficient period of time to observe both immediate and delayed toxicities that could be seen in this population.

Following completion of the flexible dose titration, patients will continue solriamfetol at 300 mg daily or their maximally tolerated dose for a treatment duration of 6 weeks. For this period of the study, 8 weeks has been selected to allow for time to observe both short term improvement in patient-reported sleep as well as potentially more delayed changes in other study endpoints (i.e. fatigue, mood, neurocognition).

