Based on our prior cross-sectional study, we anticipate 30% of patients to be enrolled during adjuvant therapy (i.e. receiving oral chemotherapy), 30% during post-adjuvant surveillance (i.e. not receiving any prescribed antitumor therapy), and approximately 30% during post-recurrent disease treatment (i.e. undergoing salvage treatment with chemotherapy). This will allow for comparisons of toxicity, tolerability, and activity by timing during cancer care.

We anticipate that approximately 20-30% of patients will be taking active corticosteroids and 60% of patients will be prescribed an antiepileptic agent. This will allow us to explore differences in tolerability and activity by these important treatment parameters.

Screening assessments may be completed by telehealth visit. These will be done through MWH when able. If not able, Doximity will be used which is what is done clinically for these patients.

4. Pre-Treatment Baseline

All patients who complete written informed consent and meet eligibility criteria will be registered and will proceed with study treatment. For patients who complete consent at the time of a regularly scheduled visit they can be provided with a baseline sleep diary and actigraph device to complete the Pre-Treatment sleep diary and actigraphy prior to Visit 1 (V1). For patients who elect to take consider study enrollment and return at a later date, sleep diary and actigraphy can be completed after (in the first 7 days after) Visit 1 (V1).

Enrolled patients will complete the pre-treatment study assessments (Section 6.7). Patients will be instructed to complete a 1-week pre-treatment baseline assessment with 7-day sleep diary that records time in bed, time awake, and estimated hours of sleep among other items (Appendix Q) as well as 7-day actigraphy (see Section 7.8.2).

Patients will either return to clinic or receive a telephone call from the study nurse, study coordinator, or study team at the end of this pre-treatment baseline week (Day 7+1 day) to record the completion of pre-treatment baseline actigraphy and sleep diary.

Baseline visit will be performed in-person.

5. Flexible Dosing Titration

Upon completion of pre-treatment baseline assessments, patients will begin flexible dosing titration. All patients will begin solriamfetol 75 mg p.o. once daily. The dose will be titrated every

7 days (+1 day) to 150 mg daily and then 300 mg daily unless the patient experiences symptomatic dose-limiting toxicity.

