Adverse events will be assessed by telephone call completed on D8+1 day, D15+1 day, and D22+1 day. Patients will be assessed in clinic at D29+7 days. Patients who report a symptomatic dose-limiting toxicity will de-escalate treatment back to the highest previously tolerated dose and will be seen for V2.

6. Fixed Dose Drug Continuation

At the completion of the flexible dose titration, patients will be seen for a routine study visit (V2) or via telehealth visit to document adverse events at the completion of flexible dosing, review sleep diary and actigraphy, and complete V2 assessments. Data from this interim time point may be used to clarify the trajectory of improvement, decline, and no change in study assessments. Patients will then proceed with fixed dose treatment at 300 mg p.o. once daily or the maximum tolerated dose for that patient.

Fixed dose drug continuation will be continued for 6 weeks. Patients will complete a sleep diary for the first 7 and last 7 days of fixed dose treatment; actigraphy will be collected continuously. At the completion of fixed dose treatment, patients will be seen for V3 study assessments (Section 6.7).

7. 30 Day Follow Up

All patients will be followed for 30 days following the completion of treatment to assess for delayed toxicity. Adverse events will be recorded at this 30 day follow up visit. If the patient is unable to return for this visit, adverse events will be recorded by telephone or telehealth visit.

8. Study Assessments

Assessment of sleep, neuro-cognitive function, fatigue, mood and quality of life will be assessed at baseline (V1) and at the end of the fixed-dose drug continuation phase of the study (V3). Given that patient drop out could occur during the course of the study treatment, study assessments that are not subject to significant practice and/or repeated measure effects will also be assessed after the flexible dose titration period (V2).

The following assessments will be performed:

1. Patient-reported outcome measures (PROMs) for sleep:

Changes in patient-reported outcomes measures (PROMs) are pivotal to cancer control drug approval.

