A DLT is defined as a clinically-significant AE or abnormal laboratory value assessed as unrelated to disease progression, intercurrent illness, or concomitant medications and which meets any of the criteria below. Based on the prior studies of solriamfetol in patients with narcolepsy and obstructive sleep apnea, treatment is anticipated to be safe at all doses. In the prior phase 2a study, no patient had to discontinue the study treatment due to a treatment-related DLT.⁴⁷ In the prior phase 2b study, in patients who experienced an AE requiring discontinuation of solriamfetol, the AEs were not deemed to be related to the study medication. In the prior phase 3 study, 9 patients (9%) including one in the 75 mg arm, 3 in the 150 mg arm, and 5 in the 300 mg arm required discontinuation due to treatment related AEs.⁴⁵

In prior studies, common adverse events include that have not required dose medication include headache (9-16%), nausea (12-14%), diarrhea (11%), decreased appetite (6-14%), anxiety (6-11%), chest discomfort (9%), insomnia (6%), muscle tightness (6%), nasopharyngitis (5-14%), and dry mouth (5-10%).

For this study, treatment-related DLTs are defined below. Dose limiting toxicities must have an attribution of possible, probable, or definite to solriamfetol. For patients experiencing a DLT during the dose escalation period, solriamfetol will be held. If the patient recovers (\leq grade 1 [or tolerable grade 2 for non-hematologic toxicity] or \leq baseline), a dose reduction (1 dose level reduction) is required. The patient will proceed with 7-days of drug treatment at the new dose level and reassessed. If there is no evidence of AE then the patient will proceed to the fixed dose drug continuation phase of the study at that dose.

If there is any question or clarification required concerning a potential DLT, the treating clinician should contact the Study Chair to determine the patient's DLT status. The Study Chair will make the final decision.

- **Hematological toxicities** are not expected with this agent, must NOT be attributed to another source, and will be considered dose limiting only if any of the following occur and are probably or definitely attributed to solriamfetol:
 - ANC of < 500/mm³
 - Platelets < 25,000/mm³
 - Febrile neutropenia
- Note: Grade 3 or 4 lymphopenia will not be considered a DLT.
- **Central nervous system toxicities** will be considered dose limiting only if any of the following occur:

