 - ≥ Grade 2 central nervous system (CNS) ischemia will be considered a DLT
 - ≥ Grade 2 neurological toxicities that interfere with activities of daily living and do not resolve spontaneously with steroids, anticonvulsants, or electrolyte correction within 7 days will be considered a DLT
 - Symptomatic CNS hemorrhage of any grade will be considered a DLT
 - ≥ Grade 3 seizure only if the patient requires inpatient hospitalization for medical intervention. A breakthrough seizure that is managed with minor antiepileptic drug modification will not be considered a DLT. Contact the Study Chair for clarification as needed.
- **Grade 3 and 4 non-hematological, non-CNS toxicities** will be considered dose limiting with the following exceptions:
 - Grade 3 nausea, vomiting, or diarrhea without sufficient prophylaxis with a duration <3 days
 - Insomnia
 - Alopecia
 - Fatigue
 - Grade 3 hyperglycemia that is reversible and without clinical symptoms
 - Grade 3 electrolyte disturbances that are asymptomatic and reversible within 3 days, and do not re-occur upon continuing or re-initiation at the same dose
 - Grade 3 or 4 hypophosphatemia, unless considered clinically relevant
 - Grade 3 or 4 elevations in alkaline phosphatase
 - Grade 3 hypertension unless inpatient hospitalization is required
 - A subject's first episode of deep venous thrombosis (DVT) or pulmonary embolism will not require dose modification

For patients who have begun the fixed dose drug continuation phase and experience a new dose-limiting toxicity, the study medication will be held until the DLT has resolved. If the DLT resolves within 14 days, the patient may resume therapy at the prior dose level (1 dose level reduction). If an additional dose reduction is required, the study medication should be discontinued.

Dose escalation will proceed for each patient according to the following scheme:

Dose Level	Solriamfetol
+1	75 mg, p.o. once daily
+2	150 mg, p.o. once daily
+3	300 mg, p.o. once daily

For patients who experience a dose limiting toxicity, the study drug will be de-escalated to the last tolerated dose. For patients who experience a dose-limiting toxicity at dose level +1, treatment will be discontinued and the patient will not receive further treatment.

2. Other Agent(s)

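### A disabling neurological toxicity needs 7 days to become a DLT while the dose rises every 7 days, and the dose level of a DLT confirmed after escalation is undefined

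*Combined protocol and SAP*

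**What the plan says.** **DLT definition (7.9.1).** CNS toxicities are dose limiting only if they meet a listed item. Grade 2 or higher ischemia, symptomatic hemorrhage, and grade 3 or higher seizure needing hospital admission carry no waiting period. The remaining item covers grade 2 or higher neurological toxicities that interfere with daily living and that "do not resolve spontaneously with steroids, anticonvulsants, or electrolyte correction within 7 days will be considered a DLT". The separate rule for grade 3 and 4 events excludes CNS toxicities.

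**Escalation (7.1, 7.5).** Dosing starts at 75 mg, "escalating after 7 days (1 week) to 150 mg daily and then after 7 days to 300 mg daily". Section 7.5 titrates every "7 days (+1 day) to 150 mg daily and then 300 mg daily unless the patient experiences symptomatic dose-limiting toxicity". Section 7.1 defends the step length: "7 days has been selected to provide a sufficient period of time to observe both immediate and delayed toxicities". Section 7.5 also sets the contacts: "Adverse events will be assessed by telephone call completed on D8+1 day, D15+1 day, and D22+1 day".

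**After a DLT.** Section 7.9.1 states: "For patients experiencing a DLT during the dose escalation period, solriamfetol will be held". On recovery the dose drops one level, the patient takes 7 days at that level and is reassessed, and fixed dosing follows if no adverse event is seen. Sections 7.1 and 7.5 describe a shorter path: back to the last or highest tolerated dose and on to the next phase or visit V2. At the lowest level 7.9.1 says: "For patients who experience a dose-limiting toxicity at dose level +1, treatment will be discontinued".

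**Analysis (13.1).** Adverse events are tabulated for each dose and compared across doses by chi-squared or Fisher's exact test. No rule covers an event that spans two doses.

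**The concern.** The persistence window and the dose step have the same length. An event that begins partway through a step is still inside its window when the escalation decision falls due, so it is not yet a DLT and the written rule moves the patient up with the toxicity unresolved. The criterion may then be met at the higher dose, and the plan does not say whether the DLT belongs to the dose at onset or the dose at confirmation. That choice decides what happens to the patient.

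The matter is close to the purpose of the trial. The primary hypothesis (2.1) is that "significant confusion/ altered mental status, seizures, or other side effects will not be more common at the 300 mg daily dose" than at the lower doses, and the rationale (1.6) gives sensitivity to psychoactive drugs and drug-induced cognitive dysfunction as reasons to study safety first. At stake are the patient-specific tolerated dose carried into the 6-week fixed phase and the clarity of the by-dose adverse event table.

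**Working it through.** **Inputs.** Persistence window 7 days (7.9.1). Step 7 days, +1 allowed (7.1, 7.5). Doses start on D8 (75 mg), D15 (150 mg) and D22 (300 mg); fixed dosing starts on D29 (7.2, 7.5). Onset timing is not given anywhere and is assumed below.

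**The plan's own figure.** (15 - 8) + (22 - 15) + (29 - 22) = 7 + 7 + 7 = 21 days, which matches the stated 3 weeks.

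**When the criterion is met.** Let onset fall on step day d. Seven days are complete on step day d + 7. Escalation falls on step day 8, or step day 9 if the +1 day is used. The criterion comes too late when:

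- strict step: d + 7 > 8, so d = 2 to 7, which is 6 of 7 onset days;
- +1 day used: d + 7 > 9, so d = 3 to 8, which is 6 of 8 onset days.

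**Uniform onset.** 6/7 = 86% on the strict step and 6/8 = 75% with the +1 day. If all 7 days must have passed, so that the criterion is met on day d + 8, the shares are 7/7 = 100% and 7/8 = 88%.

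**Front-loaded onset.** Let the chance of onset on day d be proportional to q^(d-1). The late share is 1 - 1/(sum of q^k, k = 0 to 6) on the strict step and 1 - (1 + q)/(sum of q^k, k = 0 to 7) with the +1 day. For q = 0.6 on the strict step the sum is 2.430, and 1 - 1/2.430 = 0.588.

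| q | Strict step | +1 day used |
|---|---|---|
| 1 (uniform) | 86% | 75% |
| 0.8 | 75% | 57% |
| 0.6 | 59% | 35% |
| 0.5 | 50% | 25% |
| 0.3 | 30% | 9% |

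The late share is below one half once more than half of the events start on day 1 of a step (days 1-2 with the +1 day).

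**One patient followed through the text.** A qualifying toxicity starts on D11 at 75 mg. At the D15 call 15 - 11 = 4 days have passed, so there is no DLT and the dose goes to 150 mg. The window closes on 11 + 7 = D18, at 150 mg.

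- Read as a DLT at level +2: hold, recovery, reduction to 75 mg (the dose at which the event began), 7 days, reassessment.
- Read as a DLT at level +1: discontinuation.

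The same happens one step higher. Onset on D18 at 150 mg, escalation on D22, criterion met on D25 at 300 mg: the one-level reduction leads to 150 mg on one reading and 75 mg on the other. At 300 mg there is no further escalation to block.

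**Recording.** The telephone script (Appendix T) asks about the past week on the current dose. The D11 event would be reported on D15 against 75 mg and, if it persists, on D22 against 150 mg. Section 13.1 does not say whether that is one event or two.

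**The case against.** A reader might infer that these events are counted at the wrong dose. The documents do not support that. Section 13.1 tabulates adverse events, not DLTs, and Appendix T collects symptoms against the current dose, so the D11 event can be recorded at 75 mg whatever the date of DLT confirmation. The detectable proportions in 13.4 are for the combined dosage, and the study is described there as mainly descriptive. What remains is narrower: a persisting event may appear under two doses.

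A reader might also infer that nothing can stop the next escalation. Section 7.9.1 refers questions about a potential DLT to the Study Chair, whose decision is final, and 7.11 anticipates treatment delays for adverse events and permits stopping for unacceptable events or on the investigator's judgment. This stands: the gap is in the written DLT rule, not in every route open to the clinician. But at the D15 call the criterion is plainly unmet, and no section tells anyone to defer escalation.

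Nor does it follow that the tolerated dose will be wrong. The reassessment week in 7.9.1 may catch a recurrence, and a dose with an ongoing disabling toxicity might not count as tolerated. That check comes only after the higher dose has been given, and 7.1 and 7.5 describe a path without it. The one-level reduction and the return to a tolerated dose can also point to different doses.

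On scope, the documents do not say that confusion falls under the neurological item, and 1.6 lists cognitive and neurological toxicities separately. The point is therefore confined to events that do fall under it.

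**Conclusion.** The point holds for the general neurological item in 7.9.1, at 75 mg and 150 mg. Under the written DLT rule, onset after the first day of a step (the first two days with the +1 day) cannot block the next escalation. The existence of this gap rests on the calendar alone. Its size depends on onset timing: 86% or 75% of such events if uniform, about 50-75% or 25-57% for the moderately front-loaded cases (q = 0.8 to 0.5), and less if onset is steeper still. The documents give neither the timing nor an expected number of such events, so no count of affected patients can be derived.

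The dose level of a DLT confirmed after escalation is undefined, and for onset at 75 mg the two readings lead to reduction with reassessment or to discontinuation. The patient-specific tolerated dose could therefore be set one level too high, and a persisting event could be recorded at two doses in the primary table. The claim in 7.1 that 7 days is long enough to observe delayed toxicity does not hold for an item that itself takes 7 days to be met.

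**What to change.** **Protocol.** Reconcile 7.1, 7.5 and 7.9.1 so that the 7-day resolution window, the 7-day escalation step, the path after a DLT, and the dose level of a DLT confirmed after escalation agree with one another. The clinical solution, including which level such a DLT belongs to for treatment purposes, is for the sponsor.

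**Analysis.** In 13.1, state that for analysis each adverse event is assigned to the dose at onset and counted once. Because this convention credits an event that worsens after escalation to the lower dose, also state how a later rise in grade is reported. This is a tabulation rule and does not settle the treatment question above.

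**Cost.** A wording amendment. The titration diary (Appendix F) already records date, dose and side effects by day, to be used with the adverse event log (Appendix E). Depending on the sponsor's solution, a few patients may spend some extra days in titration.

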Abdominal Pain	5 (2)	18 (3)	3 (3)	6 (3)	2 (2)	12 (3)
Constipation	2 (<1.0)	12 (2)	1 (<1.0)	6 (3)	1 (<1.0)	6 (2)
Vomiting	2 (<1.0)	6 (1)	1 (<1.0)	2 (<1.0)	1 (<1.0)	4 (1)
General Disorders and Administration Site Conditions						
Feeling Jittery	0	17 (3)	0	3 (1)	0	14 (4)
Chest discomfort	0	10 (2)	0	1 (<1.0)	0	9 (3)
Investigations						
Heart rate increased	0	8 (1)	0	5 (2)	0	3 (<1.0)
Blood Pressure increased	1 (<1.0)	7 (1)	1 (<1.0)	3 (1)	0	4 (1)
Weight decreased	0	7 (1)	0	5 (2)	0	2 (<1.0)
Metabolism and Nutrition Disorders						
Decreased appetite	2 (<1.0)	52 (9)	1 (<1.0)	25 (11)	1 (<1.0)	27 (8)
Nervous System Disorders						
Headache	18 (8)	84 (15)	8 (7)	46 (21)	10 (8)	38 (11)
Dizziness	4 (2)	19 (3)	3 (3)	9 (4)	1 (<1.0)	10 (3)
Psychiatric Disorders						
Anxiety	1 (<1.0)	39 (7)	1 (<1.0)	14 (6)	0	25 (7)
Insomniac	7 (3)	33 (6)	4 (4)	17 (8)	3 (3)	16 (5)
Irritability	1 (<1.0)	13 (2)	1 (<1.0)	5 (2)	0	8 (2)
Bruxism	0	8 (1)	0	4 (2)	0	4 (1)
Agitation	1 (<1.0)	7 (1)	0	4 (2)	1 (<1.0)	3 (<1.0)
Respiratory, Thoracic and Mediastinal Disorders						
Cough	0	10 (2)	0	3 (1)	0	7 (2)
Skin and Subcutaneous Tissue Disorders						
Hyperhidrosis	0	9 (2)	0	3 (1)	0	6 (2)
Vascular Disorders						
Hypertension	0	6 (1)	0	0	0	6 (2)

Adverse events were coded using the Medical Dictionary for Regulatory Activities (MedDRA), Version 18.0.

Protocol version date 05-19-21

Page 35 of 83

Percentages are subject incidences based on N, number of subjects within each treatment group in safety population treated in 12-week randomized studies ADX-N05 202, 14-002 and 14-003. Common adverse reactions are those occurring at a rate of $\geq 1\%$ in the combined JZP-110 treatment group and higher than the placebo rate. Events occurring at a rate of $> 1\%$ were rounded to the nearest whole percent. Events occurring $< 1\%$ are noted as such.^a Abdominal pain is a combined term of 'abdominal pain,' 'abdominal pain upper,' and 'abdominal discomfort.'^b Adverse reaction 'Headache' is a combined term of 'headache,' 'tension headache,' and 'head discomfort.'^c Insomnia' is a combined term of 'insomnia,' 'initial insomnia,' 'middle insomnia,' and 'terminal insomnia.'

Adverse Event Characteristics

- **CTCAE term (AE description) and grade:** The descriptions and grading scales found in the revised NCI Common Terminology Criteria for Adverse Events (CTCAE) version 5.0 will be utilized for AE reporting. All appropriate treatment areas should have access to a copy of the CTCAE version 5.0. A copy of the CTCAE version 5.0 can be downloaded from the CTEP web site (<http://ctep.cancer.gov>).
- **'Expectedness':** AEs can be 'Unexpected' or 'Expected' (see Section 7.1 above) for expedited reporting purposes only.
- **Attribution of the AE:**
 - Definite – The AE is **clearly related** to the study treatment.
 - Probable – The AE is **likely related** to the study treatment.
 - Possible – The AE **may be related** to the study treatment.
 - Unlikely – The AE is **doubtfully related** to the study treatment.
 - Unrelated – The AE is **clearly NOT related** to the study treatment.

2. DSMC SAE Reporting Requirements

The Data and Safety Monitoring Committee (DSMC) is responsible for reviewing SAEs for WFBCCC Institutional studies as outlined in Appendix B. DSMC currently requires that all unexpected 4 and all grade 5 SAEs on these trials be reported to them for review. All WFBCCC Clinical Research Management (CRM) staff members assisting a Principal Investigator in investigating, documenting and reporting an SAE qualifying for DSMC reporting are responsible for informing a clinical member of the DSMC as well as the entire committee via the email notification procedure of the occurrence of an SAE.

3. WFUHS IRB AE Reporting Requirements

Any unanticipated problems involving risks to subjects or others and adverse events shall be promptly reported to the IRB, according to institutional policy. Reporting to the IRB is required regardless of the funding source, study sponsor, or whether the event involves an investigational or marketed drug, biologic or device. Reportable events are not limited to physical injury, but include psychological, economic and social harm. Reportable events may arise as a result of drugs, biological agents, devices, procedures or other interventions, or as a result of questionnaires, surveys, observations or other interactions with research subjects.

All members of the research team are responsible for the appropriate reporting to the IRB and other applicable parties of unanticipated problems involving risk to subjects or others. The Principal Investigator, however, is ultimately responsible for ensuring the prompt reporting of unanticipated problems involving risk to subjects or others to the IRB. The Principal Investigator is also responsible for ensuring that all reported unanticipated risks to subjects and others which they receive are reviewed to determine whether the report represents a change in the risks

and/or benefits to study participants, and whether any changes in the informed consent, protocol or other study-related documents are required.

Any unanticipated problems involving risks to subjects or others occurring at a site where the study has been approved by the WFUHS IRB (internal events) must be reported to the WFUHS IRB within 7 calendar days of the investigator or other members of the study team becoming aware of the event.

Any unanticipated problems involving risks to subjects or others occurring at another site conducting the same study that has been approved by the WFUHS IRB (external events) must be reported to the WFUHS IRB within 7 calendar days of the investigator or other members of the study team becoming aware of the event.

Any event, incident, experience, or outcome that alters the risk versus potential benefit of the research and as a result warrants a substantive change in the research protocol or informed consent process/document in order to insure the safety, rights or welfare of research subjects.

4. Sponsor Reporting Requirements

WFBMC will and will ensure that the Investigator complies with Applicable Law in connection with the study, including but not limited to providing all adverse drug experience reports and notifications by the relevant Governmental Authority.

All serious adverse events that require reporting per the Protocol and which occur in a subject who received the Product as part of the study will be reported by email ([contact]) to Jazz Pharmaceuticals not later than 1 business day following WFBMCs receipt of notice of such occurrence. In addition, WFBMC will ensure that the Investigator provides a copy of all final reports regarding such adverse events that are provided by WFBMC or Investigator to the relevant Governmental Authority, which reports will be provided by email ([contact]) to Jazz Pharmaceuticals at the time of submission to the Governmental Authority. All other adverse events will be reported to Jazz Pharmaceuticals ([contact]) in summary or line-item form upon written request and at the conclusion of the study.

11 Pharmaceutical Information

A list of the adverse events and potential risks associated with the investigational or commercial agents administered in this study can be found in Section 9.0.

1. Pharmaceutical Accountability

[figure not shown]
Drug accountability logs will be maintained for all agents used under this protocol. These logs shall record quantities of study drug received and quantities dispensed to patients, including lot number, date dispensed, patient identifier number, patient initials, protocol number, dose, quantity returned, balance remaining, and the initials of the person dispensing the medication.

2. Solriamfetol⁴⁴

Chemical Name: (R)-2-amino-3-phenylpropylcarbamate hydrochloride

Other Names: JZP-110, ADX-N05.

Chemical Structure:

Pharmaceutical Properties: solriamfetol is a late-stage investigational wakefulness promoting agent in clinical development for the treatment of excessive daytime sleepiness (EDS) in adult patients with conditions including narcolepsy or obstructive sleep apnea. Solriamfetol is a phenylalanine derivative with dopaminergic and noradrenergic activity. Its mechanism of action, although not fully determined, includes low potency dopamine and norepinephrine reuptake inhibition.⁴⁴ It is distinct from modafinil and traditional stimulants used in patients with EDS.

Formulations: solriamfetol is formulated as an immediate release tablet available in 75 mg, 150 mg, and 300 mg strengths. The agent is supplied by Jazz Pharmaceuticals, INC. Packaging?

Route of Administration: Oral, given with or without food. Each dose should be taken with 8 ounces (240 mL) of water.

Storage Requirements: solriamfetol tablets are to be stored at room-temperature conditions, 15°C to 30°C (59°F to 86°F).

Stability: Studies are ongoing to monitor the stability of solriamfetol tablets.

12 Data Management

Informed consent document	EPIC
Protocol registration form	OnCore
Adverse Events Log (Appendix E)	OnCore
Patient Drug Diary (Appendix F)	
Fixed Dose Patient Drug Diary (Appendix G)	
Epworth Sleepiness Scale (Appendix H)	
Pittsburgh Sleep Quality Index (Appendix I)	
Brief Fatigue Inventory (Appendix J)	
Cancer Fatigue Scale (Appendix K)	
Beck's Depression Inventory (Appendix L)	
Neurocognitive Battery Form (Appendix M)	
FACT-Br (Appendix N)	
Concurrent Medication (Appendix O)	OnCore
Off-Study Form (Appendix P)	OnCore
MR Imaging Record (Appendix Q)	
Sleep Diary and Actigraphy Record (Appendix R)	
Glioma History (Appendix S)	

13 Statistical Considerations

This is a single-arm, open label, non-randomized safety study in patients with stable glioma disease. The primary outcome is safety of oral solriamfetol as doses of 75 mg daily, 150 mg daily and 300 mg daily. Secondary outcomes include ESS score, PSQI score, a composite neurocognitive battery score, FSS score, BDI score, and FACT-Br score.

1. Analysis of Primary Objective

For the primary outcome, NCI Common Terminology Criteria for Adverse Events (CTCAE) version 5.0 will be used for scoring toxicity and adverse events.

The severity and frequency of toxicity and adverse events for each dose of solriamfetol will be tabulated using descriptive statistics. The proportions of subjects who experienced grade 3 or above toxicities will be estimated, along with 95% confidence intervals by each type of toxicity.

To compare the safety of solriamfetol at 75 mg daily, 150 mg daily, 300 mg daily, chi-squared statistics will be used. If there are some cells with expected value <5 , Fisher's exact test will be used for the comparison.

2. Analysis of Secondary Objective

For the secondary outcomes, descriptive statistics will be performed for each of the outcome measures. Changes in pre- and post-treatment scores will be assessed and compared using the pair-t tests if the changes follow a normal distribution and using the Wilcoxon signed rank tests if the changes do not follow a normal distribution. For the comparison between the change in ESS score in the study patients and the published change score in patients with obstructive sleep apnea, we will use the one sample t-test for this comparison.

3. Analysis of Exploratory Objective

13.3.1 To explore the dose response effect of solriamfetol on actigraphy, linear regression models will be used where the dosage will be treated as an ordinal variable.

Transformation of actigraphy will be performed to satisfy the normality assumption if needed.

13.3.2 The analysis will be the same as that specified in 13.1.

4. Power and Sample Size

We plan to recruit around 36 participants.

In the prior phase 2a and phase 2b studies in patients with narcolepsy which had similar sample sizes, no patients in the phase 2a and three patients in the phase 2b study required discontinuation of study medication, though two of these discontinuations were not attributed to the study drug.^{46,47} In the prior phase 3 study, 9 patients (9%) including one in the 75 mg arm, 3 in the 150 mg arm, and 5 in the 300 mg arm required discontinuation due to treatment related AEs.⁴⁵ In the current study, 36 patients will receive 75 mg daily dosing. We conservatively estimate that at least 33 patients will escalate to 150 mg daily, and at least 30 patients will escalate to receive 300 mg daily. These estimates are felt to be overly conservative based on data from these prior studies in patients narcolepsy.

From prior studies, the most common adverse event proportions range from 10% to 20%. Assuming 10% and 20% of adverse event proportion, the detectable proportions for the combined dosage are 24% and 36%, respectively, in order to reach 80% power at a significance level of 0.1 (given the pilot nature of this study) and a two-sided test. These detectable proportions are reasonable. If we observe an adverse event proportion in the patients with primary gliomas that is higher than 36%, then the adverse event proportion is significantly higher than the other study populations. In practice, if an adverse event proportion is higher than 50%, then the safety/tolerability of solriamfetol needs to be questioned. We should have enough power for this primary analysis. Note that this study allows us to determine safety profiles for the 3 doses of solriamfetol. It is primarily for descriptive purpose and to generate data on safety and estimation of effect size for the design of a subsequent randomized study powered to determine drug activity. The results generated from this study will be beneficial for the future research study.

ESS score is the most important secondary outcome in this study. We also calculate the power to test whether the pre-post change is different from 0 and test whether the change is different from the pre-post change in the prior studies which recorded the pre-post changes for patients at 75 mg, 150 mg, and 300 mg. At an alpha of 0.10, a two-sided test, and cohort sample size of 36 patients, the study will have 80% power to detect the mean difference of 1.01 point ($=0.42$ standard deviation (SD)) in ESS score from the study sample. The mean differences are reasonable. We should have enough power for our analysis.

Prior studies of solriamfetol in patients with narcolepsy have demonstrated improvement in ESS scores at Week 8 of -3.4 (75 mg daily), -5.2 (150 mg daily), -6.4 (300 mg daily), and -2.1 (placebo) with baseline ESS ranging from 16.9-17.3. In patients with OSA, Week 8 improvements were -6.3 (75 mg daily), -6.9 (150 mg daily), -7.7 (300 mg daily), and -3.8 (placebo) in patients with baseline ESS ranging from 14.8 to 15.6. In our prior study mean ESS score for patients with primary brain tumors who would be eligible for the proposed study (i.e. ESS \geq 10) was 14.8 (SD: 2.4). For the current study, we will use the data from the prior OSA study as a comparator given that baseline ESS scores were similar to what we anticipate in the to-be-enrolled cohort. Based on this, the study hypothesizes that treatment with solriamfetol at 75 mg, 150 mg, or 300 mg will achieve at least a 6.3 point difference (75 mg daily) and up to 7.7 point difference (300 mg daily) in ESS scores at Week 10 (baseline vs V3). This will be compared to a null difference of 3.8 (placebo arm in OSA study). This mean change in ESS scores is clinically meaningful as has been reported.⁵³ In order to detect the differences between the mean change ESS score from the proposed study to the mean change of 3.8 in the placebo arm in OSA study, the detectable mean change needs to be greater than 5.4 in the study sample in order to reach 80% power. We hypothesize that the mean change in this study sample ranges from 6.3 to 7.7, which is higher than 5.4. We should have sufficient power to detect the difference between the mean change ESS score in our study sample and that in the placebo arm in the OSA study.

5. Estimated Accrual Rate

